3.0 Animal Studies and Previous Human Studies

Oxygen administration increases the production of F_2 -isoprostanes and isofurans *in vitro* and in mice (Figure 1).² In 435 patients from the Statin AKI Cardiac Surgery RCT we recorded oxygen administration (FIO_2) and SpO_2 prior to anesthetic induction (baseline), at induction of anesthesia, during cardiopulmonary bypass or off-pump coronary artery bypass grafting, following cardiopulmonary bypass or off-pump coronary artery bypass grafting, at ICU admission, 6-hours after ICU admission, and on postoperative day 1. In five of these subjects we maintained physiologic tissue oxygenation during surgery by limiting supplemental oxygen administration to that required to maintain $SpO_2 > 94\%$ and a $PaO_2 > 70$ mmHg (Figure 2). By doing so, both hyperoxia and hypoxia were avoided.

[figure not shown]
[figure not shown]
[figure not shown]

Figure 2
Hemoglobin Oxygen Saturation during Surgery

[figure not shown]

Fraction of Inspired Oxygen during Surgery

Oxidative stress, as measured by plasma concentrations of F_2 -isoprostanes and isofurans, was lower in the subjects administered physiologic oxygen concentrations compared to subjects who received hyperoxia, matched for risk factors for increased oxidative stress including smoking, body mass index (BMI), and use of cardiopulmonary bypass (Figure 3). In addition, none of these physiologic oxygenation preliminary subjects suffered from AKI or delirium following surgery, and duration of hospitalization was 6.3 ± 1.6 (median 5.5) days compared to 8.4 ± 4.4 (median 7) in risk-matched controls ($P < 0.001$).

Figure 3

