- Preoperative: The PI or his research nurse will offer study participation to adult patients

undergoing cardiac surgery after patients express interest to their surgeon in conjunction with a patient's preoperative surgical consultation appointment, preanesthetic evaluation appointment, or on the hospital ward. We successfully recruited subjects in these venues for 653 patients enrolled in the Statin AKI Cardiac Surgery RCT (PI: [name]).²⁷ After obtaining informed consent, patients will undergo a brief neuropsychological assessment that will include the Mini Mental Status test, the Trails B test, the CES-D Test, and the NRS 0-10 pain assessment. Patient demographics and past medical history will be documented.

- Day of surgery: anesthesia, surgery, and ICU admission will proceed irrespective of the subject's participation in the study except for the oxygen administration and monitoring and sample collection described above. Study intervention will occur in the operating room and will terminate when subject care is transferred from the anesthesiologist to the intensivist following admission to the ICU.
- Postoperative: subject postoperative ICU and hospital ward stay will proceed irrespective of the subjects' participation in the study and will be controlled by the subject's surgeon, intensivist, and consultants. Patients will be evaluated twice daily while in the ICU or for the first 3 days following surgery for level of sedation using the Richmond Agitation-Sedation Scale (RASS)²⁸ and for delirium using the CAM-ICU. Both of these assessments are standard practice in the ICUs at VUMC. On postoperative day 5 we will assess patients pain using the NRS 0-10 pain scale and the short-form McGill Pain Questionnaire.
- Subject discharge will proceed irrespective of study. In the Statin AKI Cardiac Surgery RCT, median hospital length of stay was 7 days.
- One year following surgery, we will call patients to conduct a phone interview in which we will assess neuropsychological function and activities of daily living including NRS 0-10 pain scale, short-form McGill Pain Questionnaire, the Short Blessed Test, and the CES-D Test. This assessment will take about 15 minutes to complete.

Data and Safety Monitoring Board (DSMB):

The DSMB will provide objective review of the treatment results as they relate to human safety and data quality. [REDACTED] have agreed to serve on the committee. [REDACTED], who will serve as chair, is [REDACTED]

[REDACTED]

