difference in FMD change from baseline to ICU admission between subjects randomized to hyper-oxygenation vs. physiologic oxygenation with a standard deviation of 3.0%, with a type I error rate of 0.05 (primary analysis sub-study Aim 1). We will have 94% power to detect a correlation of 0.2 or greater between intraoperative F₂-isoprostan concentrations and postoperative FMD (primary analysis sub-study Aim 2) with standard deviation of 20 pg/ml F₂I and 10 for regression errors. We will have greater than 80% power to detect a 2% difference in FMD between patients who do and do not develop postoperative delirium in the ICU, assuming a delirium incidence of 23.4% among all ROCS trial subjects, similar to that in the Statin AKI Cardiac Surgery RCT. Sub-study Aims 1 and 2 will be completed with 80 ROCS trial subjects and sub-study Aim 3 with all 200 patients.

Randomization

The study's statistician will be responsible for centralized randomization and subject assignment based on stratification in a permuted block fashion, using a sequence of blocks with sizes either two or four, where the sizes are selected uniformly at random. Randomization will be stratified by chronic kidney disease (defined as stage 3, 4, or 5 CKD [i.e., an eGFR <60 ml/min/1.73m²]) and use of cardiopulmonary bypass during surgery. Thus, there will be four randomization strata. We use the modification of diet in renal disease formula to estimate GFR for randomization stratification. This scheme provides ample subject assignment to all strata.

Data Analysis Plan

Standard graphing and screening techniques will be used to evaluate data quality. Data include patient demographics, baseline and intraoperative clinical characteristics, treatment toxicity and clinical outcomes. Summary statistics of study arms for both numerical and categorical variables will be provided to describe the study sample. Continuous variables will be summarized with the 50th (10th, 25th, 75th, 90th) percentiles, mean and standard deviation, and categorical variables will be summarized with the counts and percentages. For outcomes measured at a single time point, comparisons across randomization groups will be implemented using the Fisher's exact test or Pearson chi-square test for categorical variables, and the Wilcoxon rank sum test or Student T-test for quantitative outcomes, as appropriate. The Clopper-Pearson and Wald methods will be used to construct 95% confidence intervals for the between group effects.

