Change in serum creatinine from baseline to postoperative day 2 (Aim 1 primary endpoint) will be compared between normoxia and hyperoxia study groups using the Wilcoxon rank sum test. Plasma concentrations of F₂-isoprostanes and isofurans (Aim 2 primary endpoint) will be compared between normoxia and hyperoxia study groups using a mixed effects regression analysis, adjusting for collection time as a categorical variable (i.e., study phase). This method allows for simultaneous evaluation of multiple correlated measurements per subject, and between-subject heterogeneity in the effects of treatment on markers of oxidative stress. Specifically, we will use a random intercept and random 'slope' for treatment allocation, indexed by study subject. Analysis of the effects of treatment on change in creatinine and on oxidative stress will be repeated separately within randomization strata.

We will evaluate treatment effect on additional markers of AKI (AKI incidence using KDIGO criteria, urine concentrations of NGAL and IGFBP-7/TEMP2, use of dialysis), delirium incidence and duration (diagnosed with CAM-ICU), and myocardial damage (quantified by measuring CK-MB on the morning of the day after surgery) as secondary analyses.

To assess effect of treatment on oxygenation and perfusion we will compare SpO₂, PO₂, cerebral oxygenation, muscle oxygenation, mixed venous hemoglobin saturation, cardiac output, and arterial lactate concentrations between normoxia and hyperoxia groups using mixed effects regression analysis as described above for plasma concentrations of F₂-isoprostanes and isofurans.

We will also compare differences in ROS production, mitochondrial function, atrial fibrillation, stroke, pneumonia, wound infection, time-to-extubation, duration of ICU stay, and in-hospital mortality as well as pain scales, depression data, and neurocognitive function between normoxia and hyperoxia groups as secondary endpoints. We will compare safety endpoints myocardial infarction, transient

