We will use the Perioperative Data Warehouse (PDW), an IRB-approved research registry, and the Enterprise Data Warehouse (EDW) to extract additional clinical data. Vanderbilt's electronic healthcare records are stored in the EDW and Vanderbilt's Department of Anesthesiology healthcare records are stored in the PDW. The EDW is an electronic repository of clinical and administrative information, which is updated daily. It stores diverse sources of data from scheduling and billing systems, patient registries, nursing documentation, inpatient and outpatient clinical documentation, computerized order entry systems, pharmacy medication administration records, laboratories, radiological studies, and mortality data from the Social Security Administration Death Master File. Clinical data extracted from the PDW and the EDW data may include but are not limited to demographics (i.e., age, gender, ASA physical status, weight, height, BMI), procedures performed and associated process times (i.e. start of procedure, end of procedure, entry into pacu, discharge from pacu), type of anesthesia associated with procedures, preadmission medications, medications administered during hospital admission, laboratory data (i.e. troponin, CK-MB, creatinine, etc), physiologic information (i.e. vital signs, ventilator data, etc), diagnoses, medical history & co-morbidities, patient allergies, clinical indicators (post-operative pain scores, PONV scores, etc.), medical record (StarPanel) notes regarding any rapid response/code calls, ICU transfers, or in-hospital deaths, and clinical outcomes (i.e., hospital length of stay, mortality, ICU admission, unexpected ICU admission, rapid response/code calls, hospital readmissions, ER visits, etc.) and associated dates.

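### The Aim 2 primary mixed model adjusts only for collection time and omits both randomisation factors and BMI, which costs precision but causes neither bias nor a power shortfall

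*Combined protocol and SAP*

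**What the plan says.** - **Model.** Section 10.0, Data Analysis Plan, specifies a mixed effects regression for the Aim 2 primary endpoint, "adjusting for collection time as a categorical variable (i.e., study phase"). For the random part, "we will use a random intercept and random 'slope' for treatment allocation, indexed by study subject". No patient-level covariate and no randomisation factor is listed.
- **Randomisation.** Sections 5.0 and 10.0 stratify by chronic kidney disease and "use of cardiopulmonary bypass during surgery. Thus, there will be four randomization strata".
- **Named risk factors.** Section 3.0 says that the pilot comparison of this same endpoint was "matched for risk factors for increased oxidative stress including smoking, body mass index (BMI), and use of cardiopulmonary bypass".
- **Data available.** Section 11.0 lists, among data that may be extracted, "demographics (i.e., age, gender, ASA physical status, weight, height, BMI"). Section 6.0 adds: "Patient demographics and past medical history will be documented". Smoking is not named as a collected item.
- **Related analyses.** Section 10.0 also states: "Analysis of the effects of treatment on change in creatinine and on oxidative stress will be repeated separately within randomization strata". Its paragraph on secondary and safety endpoints allows covariates chosen for each outcome, and a propensity score approach if warranted.

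**The concern.** The treatment comparison is between patients, so any between-patient variance that baseline factors could explain stays in its standard error. A random intercept models that variance but does not remove it.

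For the stratification factors there is a second effect. Stratified randomisation keeps the between-stratum variance out of the true sampling variability of the treatment difference, but a model without the strata still counts it as error. If bypass or CKD predicts F2-isoprostanes, the reported interval will tend to be too wide.

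The protocol itself names bypass and BMI as relevant to this endpoint, bypass and CKD are known at randomisation, and section 10.0 bases inference on point estimates with 95% intervals. What is at stake is the width of the interval on a primary endpoint.

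**Working it through.** **Inputs.** Section 10.0 gives a difference of 20 pg/ml, SD 50 pg/ml, 200 subjects, 80% power and two-sided alpha 0.05. I take 100 per arm; the 1:1 ratio is inferred from two arms with blocks of two or four. Section 2.0, Aim 2, lists seven plasma sampling times. R-squared and the within-subject correlation are not given, so both are assumed over a range.

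**Step 1: the plan's own figure.** SE = 50 × √(2/100) = 7.07, and 20/7.07 = 2.83. Power from the noncentral t distribution with 198 df is 80.4% (80.7% by the normal approximation). The stated 80% reproduces, with no credit taken for covariates.

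**Step 2: adjustment, if SD 50 describes the analysed quantity.** Residual SD = 50 × √(1 − R²); three df are deducted for bypass, CKD and BMI.

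| Assumed R² | Residual SD | Power | 95% CI half-width (pg/ml) |
|---|---|---|---|
| 0 | 50.0 | 80.4% | 13.9 |
| 0.05 | 48.7 | 82.3% | 13.6 |
| 0.10 | 47.4 | 84.3% | 13.2 |
| 0.20 | 44.7 | 88.2% | 12.5 |
| 0.30 | 41.8 | 92.0% | 11.7 |

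Deducting ten df instead of three changes these powers by no more than 0.02 points.

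**Step 3: adjustment, if SD 50 is per measurement.** Take seven times, a constant 20 pg/ml effect, within-subject correlation ρ, and covariates that explain a share R²b of the between-subject variance. The variance of a subject's mean is 2500 × [ρ(1 − R²b) + (1 − ρ)/7].

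| ρ | Power, unadjusted | Power, R²b 0.20 | CI half-width, unadjusted → adjusted (pg/ml) |
|---|---|---|---|
| 0.3 | 99.4% | 99.8% | 8.8 → 8.1 |
| 0.5 | 96.1% | 98.4% | 10.5 → 9.6 |
| 0.7 | 90.4% | 95.2% | 12.0 → 10.8 |

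The power gain is smaller than the 7.8 points at R² 0.20 in Step 2 (88.2 − 80.4), but the interval still shortens.

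**Step 4: does the random intercept already do this?** Forty simulated trials used a random-intercept model with seven times, ρ = 0.5 and R²b = 0.20; the random treatment term was left out. Adding the covariate cut the mean treatment SE from 5.29 to 4.81, a variance ratio of 0.83. The Step 3 formula gives 1178.6/1428.6 = 0.825. The random intercept does not recover the loss.

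**Step 5: do the other planned analyses do it?** The within-stratum repeats give separate estimates in smaller groups and leave the primary estimate and its interval unchanged. The outcome-specific covariates sit in the secondary and safety paragraph. Its opening comparison to the primary analysis might suggest an adjusted primary, but the primary model as specified contains no such term.

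**The case against.** The strongest reply is that nothing here is an error. Randomisation makes the unadjusted comparison unbiased, the stated power is met, and stratification already balances bypass and CKD. All of that stands.

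Further parts of the reply also stand:

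- The pilot was a non-randomised comparison in which matching limited confounding. It does not show how much variance these factors explain, so the size of the gain is unknown.
- The pre-induction sample may already carry part of any stable BMI effect, so the gain beyond a baseline adjustment is also unknown.
- Bypass cannot affect the pre-induction sample, so a single bypass effect across all times would be misspecified.

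A reader might infer more than the documents support:

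- *Chance imbalance in BMI or smoking distorts the result.* It does not bias the comparison, because the unadjusted interval already allows for it.
- *The pilot's ±30 against the planning 50 implies R² = 1 − (30/50)² = 0.64.* The pilot figure concerns a difference in increase and involves five physiologic-oxygenation subjects, and the meaning of ± is not given. If it is an SD on 4 df (normality assumed), its 95% interval is about 18 to 86, which includes 50. It says nothing about R².
- *Smoking is already recorded.* It appears only in the account of the pilot matching; its collection can only be guessed from the reference to medical history.

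What the reply does not remove is that the primary model ignores the randomisation factors and that including them costs almost nothing.

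**Conclusion.** The point holds as an inexpensive improvement in precision. The Aim 2 primary model leaves out bypass, CKD and BMI, and no other planned analysis adjusts the primary estimate for them. There is no bias and no shortfall against the stated 80% power.

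The size cannot be fixed from the documents. It depends on an R-squared they do not give and on whether the SD of 50 refers to the analysed quantity or to one measurement. Over assumed R² of 0.05 to 0.30, power is about 82% to 92% on the first reading. On the second it is already about 90% or more without covariates for correlations of 0.3 to 0.7, so the benefit is mainly a shorter interval. If the three factors explain little, the gain is close to nil.

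**What to change.** In section 10.0, Data Analysis Plan, before unblinding:

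1. Add the bypass and CKD strata, as assigned at randomisation, as fixed effects in the Aim 2 primary mixed model. Using the assigned stratum rather than the bypass actually used keeps post-randomisation information out.
2. Add a bypass-by-time term.
3. Add BMI as a continuous covariate, and confirm that it will be extracted for every patient, since section 11.0 lists it only as data that may be included.
4. Add smoking only if it is confirmed to be on the data collection form.
5. Keep the model without covariates as a sensitivity analysis.

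The cost is a few sentences of SAP text and no extra patients or samples. The model gains three main effects plus six bypass-by-time contrasts over seven times (3 + 6 = 9 parameters), or ten with a two-level smoking term, against about 200 patients.

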In subjects studied in the RCT described in Aim 1, we will measure plasma concentrations of F₂-isoprostanes and isofurans sampled prior to anesthetic induction, 30 minutes after initiation of cardiopulmonary bypass or OpCAB grafting, immediately following separation from cardiopulmonary bypass, at ICU admission, 6-hours after ICU admission, and on postoperative days 1 and 2. We will measure superoxide production in whole blood collected prior to anesthetic induction, immediately following separation from cardiopulmonary bypass, and on postoperative day 1. We will compare these measurements of ROS and systemic markers of oxidative stress between subjects randomized to physiologic oxygenation or hyper-oxygenation during surgery to test the direct effect of excess oxygen exposure on oxidative stress during surgery. By comparing these data to measurements of kidney function will also test a putative but unproven mechanism of surgery-induced AKI.

By accomplishing these 2 Aims we will improve our understanding of the mechanisms of perioperative oxidative stress and postoperative morbidity while assessing any damage of hyper-oxygenation during cardiac surgery. If we determine that hyper-oxygenation increases oxidative stress and/or organ injury, subsequent multicenter studies in cardiac and non-cardiac surgery patients will be performed to validate these findings. Ultimately, we could impact the perioperative management of 30 million annual surgical patients, since the vast majority of patients are hyper-oxygenated during surgery.

Effects on Endothelial Function Sub-study

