Throughout the course of intervention, which runs from post anesthetic induction to transfer of care to the ICU staff, the subject's anesthesiologist will continuously monitor the subject's SpO₂ with every beat of the heart, as is standard care. During cardiopulmonary bypass the subject's perfusionists will continuously monitor the subject's PaO₂ with real-time inline co-oximetry, as is standard care. Anesthesiologists and perfusionists are intimately familiar with monitoring patient oxygenation and titrating oxygen delivery. The maintenance of perfusion and tissue oxygen delivery is the most basic responsibility of anesthesiologists and perfusionists.

During lung ventilation, if a subject's SpO₂ falls below 95% for 1 minute, the anesthesiologist will increase the FIO₂ by 10%. If the SpO₂ rises to > 97%, the anesthesiologist will decrease the FIO₂ by 10%. If the anesthesiologist determines the subject requires more than a 10% change in FIO₂, the adjustment of the FIO₂ is at the discretion of the anesthesiologist. The anesthesiologist will wait 2 minutes between changes in FIO₂ unless the anesthesiologist determines the subject requires more rapid titration of FIO₂ to maintain target SpO₂ 95-97%. A fresh gas flow of 2 liters/minute will be maintained throughout surgery.

During cardiopulmonary bypass, if a subject's arterial oxygen tension falls below 80 mmHg, the perfusionist will increase the FIO₂ by 10%. If the SpO₂ rises above 110 mmHg, the perfusionist will decrease the FIO₂ by 10%. If the anesthesiologist or perfusionist determines the subject requires more than a 10% change in FIO₂, the adjustment of the FIO₂ is at the discretion of the anesthesiologist and perfusionist. The perfusionist will wait 2 minutes between changes in FIO₂ unless the anesthesiologist or perfusionist determines the subject requires more rapid titration of FIO₂ to maintain target PaO₂ 80-110 mmHg.

We will evaluate the following endpoints (primary, secondary, and safety endpoints):

1. Postoperative creatinine change from baseline to postoperative day 2 (Aim 1 primary endpoint). Serum creatinine will be measured daily during hospitalization.
2. Additional markers of AKI including incidence of AKI using KDIGO criteria and urinary markers NGAL and IGFBP-7/TEMP-2.²⁴
3. Incidence and duration of delirium, measured using the Confusion Assessment Method for the ICU (CAM-ICU) twice daily while in the ICU or for at least 3 days postoperatively.²⁵

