11. One year follow-up data including assessments of cognitive function (Short Blessed Test), activities of daily living, and depression (Center for Epidemiologic Studies-Depression (CES-D) test will be obtained by phone interview, and we will examine the clinical chart for admissions, events (any renal replacement therapy), and laboratory findings (with particular focus on serum creatinine, eGFR, and urine proteinuria) in this period.
12. Safety endpoints will focus on any risk of hypoxia between study groups and will include postoperative day 1 serum CK-MB measurements (myocardial injury, defined as CK-MB greater than 50 ng/mL [10 times the upper limit of normal] and CK-MB as a continuous endpoint), postoperative myocardial infarction [defined by a new Q-wave on EKG], rates of reintubation, transient ischemic attack [defined as new deficit on neurologic exam that abates within 72 hours], stroke [defined as new deficit on neurologic exam and confirmed with radiological evidence], and death.

Urine, blood, and tissue use:

Following the placement of the arterial line and Foley catheter, 20 mL of blood and 20 mL of urine will be collected at the induction of anesthesia (baseline). We will also collect 15 mL blood and 20 mL of urine during cardiopulmonary bypass or off-pump coronary artery bypass for those subjects not requiring cardiopulmonary bypass, following cardiopulmonary bypass or off-pump coronary artery bypass, at ICU admission, 6 hours after ICU admission, and on postoperative day 1 and day 2. In total we will collect 110 mL of blood and 140 mL urine. When, after dissection of the pericardial fat, mammary artery, and incision of the atria as part of standard cardiac surgery, 1-2 g of redundant atrial tissue, 1-2 grams of discarded fat, and 1-2 g of discarded distal mammary artery will be collected for measurement of atrial myocardial function, inflammation, amyloid, oxidative stress, and arteriole vascular reactivity. Typically, this tissue is discarded, but instead we will harvest this tissue at the end of surgery. We used the same technique for collection of tissue in 450 cardiac surgery subjects in the Atrial Fibrillation and Renin Angiotensin Aldosterone System (RAAS) study (PI: [name]).²⁶

We will also collect data regarding vital signs, electroencephalographic activity, medication use, fluid input and urine output, clinical labs, and postoperative outcomes.

Sample Time-course:

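### The Aim 2 primary mixed model carries a random treatment slope that a parallel-group design cannot identify, and, read literally, it treats the pre-intervention sample as an outcome row sharing the treatment effect

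*Combined protocol and SAP*

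**What the plan says.** Section 10.0 (Data Analysis Plan) compares plasma F2-isoprostanes and isofurans between arms by mixed effects regression, "adjusting for collection time as a categorical variable (i.e., study phase". It says the method allows for correlated measurements and for "between-subject heterogeneity in the effects of treatment on markers of oxidative stress", and then gives the structure: "Specifically, we will use a random intercept and random 'slope' for treatment allocation, indexed by study subject". It states no baseline covariate and no treatment-by-time term. The oxygenation and perfusion outcomes are to be compared "using mixed effects regression analysis as described above for plasma concentrations of" the Aim 2 markers, so the structure carries over to them.

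Section 2.0 (Aim 2) lists seven plasma samples, beginning with one "sampled prior to anesthetic induction, 30 minutes after initiation of cardiopulmonary bypass or OpCAB grafting". Section 6.0 (Urine, blood, and tissue use) words the first draw slightly differently: "20 mL of blood and 20 mL of urine will be collected at the induction of anesthesia (baseline". Item 5 of the Section 6.0 endpoint list labels these markers the Aim 2 primary endpoint and includes the measurement taken before surgery along with those during and after it.

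Section 6.0 (Titration of FIO2) dates the intervention: "Throughout the course of intervention, which runs from post anesthetic induction to transfer of care to the ICU staff". Section 5.0 gives both arms 100% oxygen during induction until intubation and ventilation are verified.

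**The concern.** A random slope needs a regressor that varies within the unit carrying the slope. Allocation does not vary within a subject here, so the term has no within-subject information to draw on. The plan nevertheless presents it as dealing with heterogeneity of treatment effect. A fitted slope SD could then be published as evidence of differing responses to oxygen when the data cannot say so.

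The second matter bears on the primary estimate itself. The first sample precedes any difference in treatment. If it is an outcome row under one common treatment effect, the estimate averages in a time at which no effect is possible, and the most useful covariate in the data set is not used as one. The plan handles baseline explicitly elsewhere: Aim 1 uses change in creatinine, and the endothelial sub-study uses change scores and baseline adjustment.

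**Working it through.** **The plan's own figure.** Section 10.0 states 80% power for 20 ± 50 pg/ml with 200 subjects. Taking 100 per arm, two-sided 5% and one value per subject, SE = 50 × √(2/100) = 7.07, the ratio is 20/7.07 = 2.83, and power is 80.4% (t, 198 df). The figure reproduces.

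**Identifiability of the slope.** Let the intercept variance be s0², the slope variance s1² and their covariance c. With allocation coded 0/1 and constant within subject, the between-subject variance is

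- arm coded 0: s0²
- arm coded 1: s0² + 2c + s1²

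That is two estimable quantities for three parameters. The rank of the derivative of both arms' 7 × 7 covariance matrices with respect to the variance parameters (residual included) is:

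| Random effects | Coding of allocation | Rank / parameters |
|---|---|---|
| Correlated | constant, 0/1 or ±0.5 | 3 of 4 |
| Independent | constant, 0/1 | 3 of 3 |
| Independent | constant, ±0.5 | 2 of 3 |
| Correlated | time-varying, 0 at the pre-induction row | 4 of 4 |

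A likelihood check on one simulated data set agrees. With (s0², c, s1²) = (900, 0, 300), (900, −150, 600), (900, −300, 900) and (900, −600, 1500), the second arm's variance is always 1200 and the log-likelihood is always −6981.752.

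Independent effects with 0/1 coding can be fitted, but the slope variance is then only the excess variance of the arm coded 1. With arm variances simulated at 1250 and 1850, it came out as 1190 with one arm coded 1 and 0 with the codes swapped. Real heterogeneity can also vanish: with effect SD 30, intercept SD 50 and correlation −0.3, the treated-arm variance is 2500 + 2 × (−0.3 × 50 × 30) + 900 = 2500, the same as control.

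**What software returns.** Sixty trials were simulated with the same 20 pg/ml effect in every treated subject, so the true slope SD is 0. R's nlme gave slope SDs of 35–41 pg/ml with no warning. R's lme4, on the same data, gave 3.5–54.5 with one fit flagged singular. A profiled REML fit in Python of the same scenario gave 0.06–22. The reported value depends on the routine. In the profiled REML fits the treatment coefficient differed from the random-intercept model by at most 4e-14 and its SE by at most 0.004%.

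**The pre-induction row.** Volumes confirm seven draws: 20 + 6 × 15 = 110 mL, matching "In total we will collect 110 mL of blood and 140 mL urine". On either wording of its timing, the first draw precedes the intervention.

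Assumptions, none of them in the documents: SD 50 at every sample, complete data, a constant 20 pg/ml effect at the six later samples, and the correlations below. With complete data and a random intercept, the treatment coefficient is the difference in subject means over the rows used.

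- Seven rows: estimate (0 + 6 × 20)/7 = 17.1
- Six later rows: estimate 20.0
- SE = √(2/100) × SD of the subject-level contrast. For exchangeable r the SDs are 50√((1+6r)/7) for seven rows, 50√((1+5r)/6) for six, and 50√((1+5r)/6 − r²) for six with baseline as covariate.

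| Correlation, later / with baseline | SE: seven, six, covariate | Power %: seven, six, covariate |
|---|---|---|
| 0.3 / 0.3 | 4.47, 4.56, 4.04 | 97, 99, ≥99.8 |
| 0.5 / 0.5 | 5.35, 5.40, 4.08 | 89, 96, ≥99.8 |
| 0.7 / 0.7 | 6.09, 6.12, 3.61 | 80, 90, ≥99.8 |
| 0.5 / 0.3 | 5.11, 5.40, 4.97 | 91.6, 95.8, 98.0 |
| 0.7 / 0.3 | 5.68, 6.12, 5.74 | 85.2, 90.1, 93.4 |
| 0.7 / 0 | 5.35, 6.12, 6.12 | 89.1, 90.1, 90.1 |
| 0.3 / 0 | not shown | 98.8, 99.2, 99.2 |

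In simulation (8000 runs each), rejection under the null was 5.1–5.2% with seven rows and 4.6–5.1% with the covariate.

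**The case against.** The plan's sentence can be read as accommodating heterogeneity rather than estimating it. No heterogeneity hypothesis is set, no slope variance is promised in the results, and the identifiable part of the model is simply arm-specific variance, which is legitimate. This largely stands: it is why the slope does no harm to the treatment test. It does not rescue the term as specified, because the parameter named for heterogeneity still has no determinate value. A time-varying regressor would be identifiable, but the text specifies allocation. Even then the slope would reflect each subject's departure from the average post-intervention change in one arm, not a pure difference in treatment effect.

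A reader might infer that the planned analysis would often fail to fit. One Python routine did stop as singular in 27 of 60 simulated trials, but other routines, including those in R (the plan's software), did not reproduce this.

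A reader might also infer that the plan is silent on the pre-intervention sample. It is not: Section 6.0 places that value inside the primary endpoint, so the natural reading is an outcome row. The fair criticism concerns the consequence of that reading. The plan does not rule out a treatment-by-time term; it states none.

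Finally, the baseline matter is mainly one of efficiency and rests on assumed SDs and correlations. That is correct, and the range above shows it.

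**Conclusion.** Both parts hold, and both are worth correcting before unblinding.

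The slope result is algebraic and needs no assumption beyond allocation being constant within subject: the model cannot speak to differences in treatment effect between subjects, and a reported slope SD would be uninterpretable.

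The baseline result follows from reading Sections 6.0 and 10.0 together. A constant later effect is diluted by one seventh (20 to 17.1 pg/ml). The power gain from using baseline as a covariate runs from under 1 point to about 20 points over the correlations tabulated.

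The documents do not support a conclusion that the Aim 2 test is invalid or the trial underpowered. Type I error holds in simulation, and the stated 80% reproduces with one value per subject. Seven-row power stays at about 80% or more in every tabulated case. It falls below only at a higher assumed correlation (75.9% at exchangeable r = 0.8, normal approximation), and the documents give no correlation.

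**What to change.** In the Data Analysis Plan of Section 10.0:

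- Replace the random treatment slope with a subject random intercept or an unstructured within-subject covariance, adding arm-specific variances if wanted. Do the same in the oxygenation and perfusion models that reuse the structure.
- Delete the statement that the method addresses between-subject heterogeneity in treatment effects.
- Use the pre-induction F2-isoprostane and isofuran values as baseline covariates, or constrain the arm means to be equal at baseline, so that this sample carries no treatment effect. Align item 5 of the Section 6.0 endpoint list.
- Fix the post-baseline contrast before unblinding. The average over the six later samples is one option; the choice is the sponsor's.

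The cost is SAP and protocol wording only, since the sample is already collected. With the covariate version, subjects missing the baseline sample drop out; the equal-baseline-means version avoids this.
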